Any participant with adequate BIVV001 PK data will be included in the PK Analysis Set. A noncompartmental analysis will be performed for each participant's BIVV001 baseline PK profile. Any participant who does not have adequate PK data will be excluded from the PK analysis. An additional participant will be enrolled in the PK subgroup to ensure that at least 24 participants have adequate PK data for analysis. Instructions for wash-out and PK sampling are provided in Appendix 7, [Section 10.7.4](#).

Pharmacokinetic parameters of BIVV001 activity including but not limited to the maximum activity (C_{max}), $t_{1/2}$, total clearance (CL), total clearance at steady state (CL_{ss}), volume of distribution at steady state (V_{ss}), area under the activity-time curve (AUC), dose-normalized area under the activity-time curve (DNAUC), mean residence time (MRT), IR, trough activity (C_{trough}) and time above 1% FVIII activity measured by activated partial thromboplastin time (aPTT) clotting assay and chromogenic assay will be determined for BIVV001. Pharmacokinetic parameters will be summarized for each age cohort for BIVV001 with geometric means and their corresponding 95% CIs.

Other Secondary endpoints

All other secondary endpoints will be summarized descriptively.

The number and percentage of participants achieving trough FVIII activity levels above 1%, 3%, 5%, 10%, 15%, and 20% will be summarized. In these summaries, FVIII activity level will be based on the average trough samples (ie, nominal 168 hour time point) from each scheduled visit (Week 4, Week 13, Week 26, Week 39, Week 52) using the one-stage aPTT assay and chromogenic assay. Participants with trough samples that are outside 168 ±5 hours from the previous dose will be excluded from this analysis.

The percentage of participants with resolution of at least 1 target joint and the percentage of total target joints that are resolved at 52 weeks will be summarized. A target joint is defined as a major joint (eg, hip, elbow, wrist, shoulder, knee or ankle) into which ≥ 3 spontaneous bleeding episodes occurred in a consecutive 6-month period and resolution is achieved when ≤ 2 bleeding episodes occur into that joint during 12 months of continuous exposure.

The consumption of BIVV001 will be annualized and summarized.

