- b Washout prior to BIVV001 Day 1 dose administration is at least 96 hours (4 days) for 6 to <12 years participants and at least 72 hours (3 days) for <6 years participants. The washout period prior to Day 1 BIVV001 dose administration may be modified at the discretion of the Investigator based on individual PK data and clinical phenotype in consultation with the medical monitor. Separate samples for anti-rFVIII Fc-VWF-XTEN antibody testing will be collected at the same timepoint when any samples are collected for inhibitor testing (including samples for suspected inhibitor and confirmatory inhibitor tests).
- c Participants should schedule their study visits to be 7 ±1 day after the previous prophylactic dose of BIVV001.
- d Unscheduled visits may be necessary during the study to repeat any blood sampling if required, or at the discretion of the Investigator. If a participant has an unscheduled visit, the Investigator will record data as appropriate based on the purpose of the visit. Vital signs should be taken after the participant has been resting supine for 5 minutes. If BIVV001 is being administered at an unscheduled visit, vital signs will be measured pre-injection and 30 (+/-15) minutes from the start of injection. If an unscheduled visit occurs only for purposes of prophylactic administration of BIVV001, collection of physical exam and vital sign data is not required.
- e This call or visit will occur 2 to 3 weeks after the last dose of BIVV001, unless the participant enrolls in the open-label extension study.
- f Informed consent from the participant's legal guardian MUST be obtained prior to any study-related procedures, including washout of current FVIII therapy specifically for entry into the study. Participant assent must also be obtained where applicable (according to the study site's local regulations).
- g Demographics include sex, race, ethnicity, and date of birth (year of birth only), as permitted by local regulations. Race and ethnicity will be collected for reasons described in [Section 10.1.4](#)
- h Includes hemophilia history assessment of disease severity, blood type, and Rh factor if not previously documented. For Repeat Screening Visit, update with any changes since original Screening Visit.

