The first 12 participants in each age cohort (<6 years of age to 12 years and 6 to <12 years of age) will undergo PK sampling after the first dose of BIVV001 (Baseline) (see [Table 2](#) for details). After full enrollment of the PK subgroup, optional participation in the PK subgroup is offered. All other participants will have trough and peak samples only (collected within 30 minutes prior to BIVV001 dosing and 15 (\pm 3) minutes post injection).

Participants who undergo major surgery during the study will be included in the surgery subgroup.

Study clinic visits

All enrolled participants will come in to scheduled visits at the following time points: Baseline (Day 1), Week 4, Week 13, Week 26, Week 39, and Week 52. Details of each visit are provided in [Table 1](#).

For all participants each scheduled study visit subsequent to BIVV001 Day 1 is to be arranged 7 days (\pm 1 day) after the preceding prophylaxis dose. The participant should withhold the weekly prophylaxis dose on the day of the study visit, so that it can be administered at the study visit.

The first 12 participants in each age cohort (<6 years of age to 12 years and 6 to <12 years of age) will undergo PK sampling after the first dose of BIVV001 (Baseline), including samples at Day 1, Day 2, Day 4 and Day 8 (Table 2). All other participants will have trough and peak sample only (collected within 30 minutes prior to BIVV001 dosing and 15 (\pm 3) minutes post-injection at each visit where a BIV001 injection is scheduled.

Participants will undergo efficacy and safety assessments throughout their participation in the study. Safety assessments will include testing for inhibitor development to FVIII. A Follow-up Safety Visit or Telephone Call will occur 2 to 3 weeks after the last dose of BIVV001, unless the participant enrolls in the open-label extension study. Participants will complete their End of Study (EOS) Visit 52 (\pm 7) days post-Baseline, or earlier if EOS has been declared.

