6.1.2 Study treatment schedule and administration

Instructions for the preparation and administration of BIVV001 are provided in the Pharmacy Manual and the Information for Patients.

The prophylactic treatment regimen is QW (every 7 days) dosing with 50 IU/kg BIVV001. This dose was determined based on population PK model and appropriate simulations to understand steady state kinetics of BIVV001. The aim of the 50 IU/kg QW treatment regimen is to provide sustained FVIII activity levels in the normal to mild hemophilic range and to decrease treatment burden with QW dosing.

The dosing interval in the younger age cohort (<6 years) may be reduced by 1 or 2 days if clinically warranted at the discretion of the investigator and only after consultation with the study medical monitor. For participants who have their BIVV001 dosing interval reduced, the washout period prior to inhibitor tests must be adjusted accordingly.

BIVV001 will be delivered via a slow push IV injection at a rate of administration listed in [Table 6](#) and determined by the participant's comfort level. BIVV001 formulation contains sucrose and the injection durations listed in [Table 6](#) are consistent with recommendations on infusion rates. Overall, the recommended maximum total injection time should be ≤ 15 minutes for all doses.

Table 6 - BIVV001 weight-based vial and injection rate recommendations

Participant weight	Minimum injection duration per vial	Maximum total injection time
10-<20 kg	6 minutes per vial	15 min
20-<30 kg	3 minutes per vial	15 min
≥ 30 kg	2 minutes per vial	15 min

Any missed of BIVV001 doses should be taken as soon as possible or according to the instructions of the Investigator, taking into account that 2 consecutive prophylactic doses of 50 IU/kg should be separated by a period of at least 72 hours.

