Embolic and thrombotic events are defined as arterial or venous thrombosis, confirmed by imaging.

Coronary artery thrombosis/occlusion must be confirmed by coronary angiography to be included as part of medical adjudication.

Thrombosis involving the cerebral vasculature must be confirmed by imaging such as magnetic resonance imaging venogram, computed tomography venogram, magnetic resonance angiography, or computed tomography angiography to be included as part of medical adjudication.

An indwelling central venous access device is a well-established risk factor for thrombosis (47) and thrombotic events associated with such devices will not be included as part of medical adjudication. Occlusion or malfunction of a central venous access device also will not be included as part of medical adjudication.

Infusion thrombophlebitis is a recognized complication of peripheral vein infusion (48) and will not be included as part of medical adjudication.

Pharmacokinetics

Any participant with adequate BIVV001 PK data will be included in the PK Analysis Set. A noncompartmental analysis will be performed for each participant's BIVV001 baseline PK profile. At least 24 participants will be enrolled in the PK group. Instructions for wash-out and PK sampling are provided in Appendix 7, [Section 10.7.4](#).

Pharmacokinetic parameters of BIVV001 activity including but not limited to C_{max} , CL, CL_{ss} , V_{ss} , AUC, DNAUC, MRT, IR, C_{trough} and time above 1% FVIII activity measured by aPTT clotting assay and chromogenic assay will be determined for BIVV001. Pharmacokinetic parameters will be summarized for each age cohort for BIVV001 with geometric means and their corresponding 95% CIs.

Other Secondary endpoints

All other secondary endpoints will be summarized descriptively.

The number and percentage of participants achieving trough FVIII activity levels above 1%, 3%, 5%, 10%, 15%, and 20% will be summarized. In these summaries, FVIII activity level will be based on the average trough samples (ie, nominal 168 hour time point) from each scheduled visit (Week 4, Week 13, Week 26, Week 39, Week 52) using the one-stage aPTT assay and chromogenic assay. Participants with trough samples that are outside 168 ± 5 hours from the previous dose will be excluded from this analysis.

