- No washout required. Participants should visit clinic 7 ±1 day after previous dose.
- If the participant has treated a bleeding episode since his last dose, the scheduled visit should be postponed for 7 ±1 day after previous dose.

PK Sampling

[figure not shown]
- Collection of sample at trough (immediately pre-injection) and peak at 15 ±3 mins from start of injection. If the participant treats a bleed prior to collection of the peak and trough sample collection, no repeat sampling is needed and the participant will remain in the study and collect peak and trough at the next scheduled visit.

^a The washout period may be modified at the discretion of the Investigator based on individual PK data and clinical phenotype in consultation with medical monitor

[figure not shown]

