4.4.4 Percentage of participants who maintain FVIII activity levels

The number and percentage of participants achieving steady-state trough FVIII activity levels above 1%, 3%, 5%, 10%, 15%, and 20% will be summarized by age cohort and overall. In these summaries, FVIII activity level will be based on the average trough samples (ie, nominal 168-hour time point) from each scheduled visit (Week 4, Week 13, Week 26, Week 39, Week 52) using the aPTT-based one-stage assay and chromogenic assay. Participants with trough samples that are outside 168 +/-5 hours from the previous dose will be excluded from this analysis.

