- For each assay type, a summary table of FVIII activity levels will be provided for BIVV001 at scheduled PK visits and time points for the PK subgroup (Baseline BIVV001). Summary descriptive statistics will include the number of non-missing values, mean, geometric mean, standard deviation, percent coefficient of variation, minimum, and maximum. In these summaries, values below the LLOQ will be imputed as zero.
- For each assay type, individual PK parameters will be listed for each participant and summarized descriptively for the PK subgroup (Baseline BIVV001). Any FVIII assessments flagged by the PK scientist as being implausible and excluded from computation of PK parameters will be excluded from summaries but included in listings. The listings will indicate which values, if any, were excluded from summaries. A separate listing of excluded values, together with the reason for exclusion will be provided.

In addition, for each assay type, the peak and trough concentrations will be summarized by visit for the FAS. The incremental recovery will also be summarized by visit for the FAS. Summary descriptive statistics will include the number of non-missing values, mean, geometric mean, median, Q1, Q3, standard deviation, percent coefficient of variation, minimum, and maximum. In these summaries, values below the LLOQ will be imputed as zero.

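### The Day 7 FVIII threshold endpoint (SAP 4.4.4) excludes the participant, not the off-time trough sample, so a protocol-compliant child can lose valid data

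*SAP*

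**What the plan says.** SAP 4.4.4 bases the endpoint on the average of the troughs (nominal 168 h) from Weeks 4, 13, 26, 39 and 52, by the one-stage and chromogenic assays. It then sets the timing rule: "Participants with trough samples that are outside 168 +/-5 hours from the previous dose will be excluded from this analysis". The protocol synopsis reads "Participants with trough samples that are outside 168 ±5 hours from the previous dose will be excluded from this analysis", and protocol 9.4.3 has the same sentence.

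Visit timing is wider. Footnote c to the schedule of activities (protocol 1.3) says "Participants should schedule their study visits to be 7 ±1 day after the previous prophylactic dose of BIVV001", and protocol 10.7.4 says "Participants should visit clinic 7 ±1 day after previous dose". Protocol 4.1 gives the same ±1 day for each visit after Day 1 and adds that "The participant should withhold the weekly prophylaxis dose on the day of the study visit". The trough is drawn within 30 minutes before that dose.

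For children under 6 years, protocol 6.1.2 states: "The dosing interval in the younger age cohort (<6 years) may be reduced by 1 or 2 days if clinically warranted". SAP 4.4.4 does not say how these children enter the endpoint.

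**The concern.** A child contributes up to five troughs, but the rule acts on the child. Nothing says how many troughs must be off-window to trigger it, or that in-window troughs are kept. If any one is enough, a child who attended every visit within the permitted ±1 day can be removed along with correctly timed samples. Two programmers could derive different denominators from the same sentence.

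The plan already has a finer approach for a related purpose. In the PK summaries of SAP 4.8.1, "Any FVIII assessments flagged by the PK scientist as being implausible and excluded from computation of PK parameters will be excluded from summaries": there the assessment is dropped, not the participant.

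At stake is the denominator of a named secondary efficacy endpoint, with only about 25 completers planned per age cohort. A child under 6 whose interval is shortened mid-study would, under the any-trough reading, also lose the earlier valid 168-hour troughs. That loss falls on one cohort only. Bias from it is possible but cannot be quantified from the documents.

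**Working it through.** The documents give no expected number for this endpoint, so there is no plan figure to reproduce.

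**Windows.** Analysis window: 168 ± 5 h = 163 to 173 h, 10 h wide. Permitted visits: 7 ± 1 days = 144 to 192 h, 48 h wide. Ratio: 10/48 = 20.8%. A compliant trough can lie 24 − 5 = 19 h outside the analysis window.

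**Assumptions (not in the documents).** Five troughs per child; normal timing centred on 168 h with SD 2, 3 or 6 h; any off-window trough removes the child under the participant rule; at least one in-window trough keeps the child under the sample rule.

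**Formulas for independent visits.** p = P(|t − 168| ≤ 5) = 0.988, 0.904 and 0.595 for SD 2, 3 and 6 h.
- Participant rule keeps p^5. At SD 3 h: 0.904^5 = 0.605.
- Sample rule keeps 1 − (1 − p)^5. At SD 6 h: 1 − 0.405^5 = 0.989.
- Share of valid in-window troughs discarded by the participant rule: 1 − p^4. At SD 3 h: 0.331.

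**Correlated visits.** Timing is a shared plus an independent normal part, simulated with 1,000,000 children per cell. At correlation 1 both rules keep p. Children kept, participant rule v sample rule:

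| Correlation | SD 2 h | SD 3 h | SD 6 h |
|---|---|---|---|
| 0 | 94% v >99.9% | 60.5% v >99.9% | 7.5% v 98.9% |
| 0.5 | 95% v >99.9% | 68% v 99.7% | 13% v 95% |
| 0.8 | 96% v 99.9% | 78% v 98% | 27% v 85% |
| 1 | 98.8% both | 90.4% both | 59.5% both |

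For 50 children at SD 3 h, the participant rule keeps 30, 34, 39 and 45 (correlation 0, 0.5, 0.8, 1); the sample rule keeps 50, 50, 49 and 45. Valid troughs discarded by the participant rule: 33%, 25%, 14% and 0% at SD 3 h; 87%, 79%, 55% and 0% at SD 6 h.

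**Extreme case.** If visits were spread evenly and independently over the permitted 48 h, p = 0.208. The participant rule would keep 0.208^5 = 0.04% and the sample rule 1 − 0.792^5 = 68.9%.

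**Is ±5 h reasonable?** Protocol 2.2.3.2 gives an adult half-life of 37 to 44 h. A sample taken d hours early reads 2^(d/half-life) times the 168-hour value: 1.08 to 1.10 for 5 h, 1.46 to 1.57 for 24 h (a 144-hour trough), 2.1 to 2.5 for 48 h (a 120-hour trough). Dropping off-time samples is sound, and 120- or 144-hour troughs should not count as Day 7 values. None of this requires dropping the child.

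**The case against.** **The sentence may be meant at sample level.** The level is taken from each scheduled visit, which allows a reading in which only that visit's value drops out. This stands as an ambiguity: the loss figures apply only to the any-trough reading. But the unit named is the participant in all three places, and no other section corrects it.

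**The size is assumed.** This is correct. The result runs from no gain at correlation 1 to 7.5% against 98.9%. With evenly spread visits the sample rule itself still loses about 31% of children. Under these assumptions the sample rule never keeps fewer children than the participant rule.

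**The SAP has no general sample-level convention.** This is also fair. SAP 4.8.1 concerns implausible values, not off-time ones, and the Per Protocol Set and the target-joint analysis select whole participants. The comparison with SAP 4.8.1 shows that sample-level exclusion fits the plan, not that the plan requires it.

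**One trough is a thin basis for an average.** At SD 6 h and correlation 0 to 0.8, 26% to 32% of kept children would have two or fewer in-window troughs. This is a real cost, to be met by reporting the number of troughs per child.

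**The consequence is small.** The endpoint is descriptive, and SAP 4.8.1 already summarises troughs by visit for the Full Analysis Set. Those summaries do not give the threshold percentages.

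**Conclusion.** The concern holds. As worded, the rule can remove a protocol-compliant child and his valid 168-hour troughs from a named secondary endpoint. The wording is certain; the size is not, because it rests on the any-trough reading and on assumed visit timing. At SD 3 h the participant rule would cost about 11 to 20 of 50 children for correlations from 0.8 to 0, against at most one under the sample rule; at correlation 1 each rule loses 5. No hypothesis is tested, so error rates are not involved and the primary inhibitor analysis is untouched. The ±5 h window is reasonable; only the unit of exclusion needs changing. It should be fixed before database lock.

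**What to change.** In SAP 4.4.4, make trough samples, not participants, the subject of the exclusion sentence. Then add:

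- Each child's level is the average of the remaining in-window troughs, with at least one required.
- The denominator, the samples dropped, the number of troughs per child and the children with no usable trough are reported by age cohort.
- For children under 6 years whose interval was shortened, in-window 168-hour troughs from before the change count in the main percentage. Troughs taken at 120 or 144 h do not count as Day 7 values. These children are also listed separately. A child shortened before any in-window trough is reported as having none usable.

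The SAP should say that this clarifies protocol 9.4.3 and the synopsis. Both can be aligned at the next amendment; none is needed for this alone, because protocol 9.4.1 leaves the more technical description to the SAP.

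The cost is a few sentences and one sample-level flag, with no new data. The downside is that some children are averaged over fewer than five troughs: under the same assumptions a kept child has on average 4.5 to 4.6 at SD 3 h and 3.0 to 3.5 at SD 6 h (correlation 0 to 0.8).

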4.4.5 Number of injections and dose of BIVV001 to treat a bleeding episode

The number of injections and total dose of BIVV001 (IU/kg) to treat a bleeding episode will be determined on both a per-bleeding episode and per-participant basis. A bleeding episode is considered resolved when treatment for the bleeding is no longer needed.

Per bleeding episode: The total number of injections will consider all injections, including initial and follow-up injections, in a bleeding episode. The total dose of BIVV001 will be the sum of these doses. The number of injections to treat a bleeding episode will be summarized across all

bleeding episodes both categorically $(1, 2, 3, 4, >4; 1, >1; and \le 2, >2)$ and with descriptive statistics. The total dose of BIVV001 used to treat a bleeding episode will be summarized using descriptive statistics.

Per participant: The number of injections and total dose of BIVV001 to treat each bleeding episode, as determined for the per-bleeding episode summaries, will be averaged across all bleeding episodes for each participant. The average number of injections required for resolution of a bleeding episode will be summarized both categorically (1 to <2, 2 to <3, 3 to <4, and \geq 4; and 1 to <2, \geq 2) and with descriptive statistics. The averages for the per-participant total dose of BIVV001 used to treat a bleeding episode will be summarized using descriptive statistics.

4.4.6 Percentage of bleeding episodes treated with a single injection of BIVV001

The number and percentage of bleeding episodes treated with a single injection of BIV001 will be determined on a per-bleeding episode basis. The number and percentage of bleeding episodes treated with a single injection of BIVV001 will be summarized by age group and overall for the FAS.

4.4.7 Assessment of response to BIVV001 treatment of bleeding episodes

Participants will provide an assessment of response to each injection of BIVV001 for treating a bleed using a 4-point scale of excellent, good, moderate, and none, based on ISTH standardized definitions in hemophilia (1). Response categories of excellent and good will be presented combined as well as individually.

The assessment of response will be summarized first on a per injection basis. The number and percentage of injections in each response category will be tabulated based on all injections; percentages will be based on the total number of injections for treating a bleed for which a response was provided.

As a supplemental analysis, the assessment of response will also be summarized on a per bleeding episode basis by presenting the number and percentage of first injections to treat a bleeding episode for which the response to the treatment was categorized as excellent, good, moderate, or no response. Percentages will be based on the number of bleeding episodes for which a response was provided for the first injection.

The participant's assessment of response during the efficacy period will be summarized by age cohort as well as overall for the FAS.

